#### **4.4.7 Restrictions during the study**

##### **4.4.7.1 Contraception**

Females of childbearing potential who are sexually active with a nonsterilised male partner must use 2 methods of effective contraception from screening, and must agree to continue using such precautions for 180 days after the final dose of investigational product. Periodic abstinence, the rhythm method, and the withdrawal method are not acceptable methods of birth control.

- Females of childbearing potential are defined as those who are not surgically sterile (i.e., bilateral tubal ligation, bilateral oophorectomy, or complete hysterectomy) or postmenopausal (defined as 12 months with no menses without an alternative medical cause).
- Subjects must use 2 acceptable methods of effective contraception as described in the table below.
- Nonsterilised males who are sexually active with a female partner of childbearing potential must use 2 acceptable methods of effective contraception (see Table 1) from Day 1 and for 90 days after receipt of the final dose of investigational product.

Quad-Shot Radiotherapy in Combination with Immune Checkpoint Inhibition for  
Advanced/Recurrent Head and Neck Cancer  
Wake Forest Baptist Comprehensive Cancer Center  
WFBCCC60320

**Effective methods of contraception (two methods must be used)**

Barrier Methods	Intrauterine Device Methods	Hormonal Methods
Male condom plus spermicide Cap plus spermicide	Copper T Progesterone T a	Implants Hormone shot or injection Combined pill Minipill Patch
Diaphragm plus spermicide	Levonorgestrel-releasing intrauterine system (e.g., Mirena ® ) a	

a This is also considered a hormonal method.

**4.4.7.2 Blood donation:**

Subjects should not donate blood while participating in this study and for at least 90 days following the last infusion of pembrolizumab.

**4.4.7.3 Concomitant treatments**

**Permitted concomitant medications**

Investigators may prescribe concomitant medications or treatments (e.g., acetaminophen, diphenhydramine) deemed necessary to provide adequate prophylactic or supportive care except for those medications identified as "excluded" as listed below.

**Excluded Concomitant Medications**

The following medications are considered exclusionary during the study.

1. Any investigational anticancer therapy
2. Any concurrent chemotherapy, radiotherapy (except palliative radiotherapy), immunotherapy, biologic or hormonal therapy for cancer treatment. Concurrent use of hormones for noncancer-related conditions (e.g., insulin for diabetes and hormone replacement therapy) is acceptable.
3. Immunosuppressive medications including, but not limited to systemic corticosteroids at doses exceeding 10 mg/day of prednisone or equivalent, methotrexate, azathioprine, and TNF- $\alpha$  blockers. Use of immunosuppressive medications for the management of investigational product-related AEs or in subjects with contrast allergies is acceptable. In addition, use of inhaled and intranasal corticosteroids is permitted. A temporary period of steroids will be allowed for different indications, at the discretion of the principal investigator (e.g., chronic obstructive pulmonary disease, nausea, a short course of prednisone that is prescribed for acute allergic situations or for prevention of an allergy to contrast substance utilized for imaging studies, etc).
4. Live attenuated vaccines within 30 days of pembrolizumab dosing (ie, 30 days prior to the first dose, during treatment with pembrolizumab and for 30 days post discontinuation of pembrolizumab. Inactivated vaccines, such as the injectable influenza vaccine, are permitted.

Quad-Shot Radiotherapy in Combination with Immune Checkpoint Inhibition for  
Advanced/Recurrent Head and Neck Cancer  
Wake Forest Baptist Comprehensive Cancer Center  
WFBCCC60320

Prohibited and Rescue Medications	
Rescue/supportive medication/class of drug:	Usage:
Concomitant medications or treatments (eg, acetaminophen or diphenhydramine) deemed necessary by the Investigator to provide adequate prophylactic or supportive care, except for those medications identified as "prohibited" as listed above	To be administered as prescribed by the Investigator
Best supportive care (including antibiotics, nutritional support, correction of metabolic disorders, optimal symptom control, and pain management.)	Should be used when necessary for all patients

#### **4.5 Other Non-study Treatments**

Other local treatments (including but not limited to radiation therapy, surgery, interventional procedures) to sites outside the QuadShot target region are allowed for local symptom palliation or in the case of limited oligometastatic or oligopressive disease.

### **5.0 Study Outcomes and Study Measures**

#### **5.1 Primary Outcome**

- 5.1.1 The overall response rate will be measured according to RECIST 1.1 (Section 7.1.3).

#### **5.2 Secondary Outcomes**

- 5.2.1 The response rate in the target lesion measured according to RECIST 1.1 (Section 7.1.3).
- 5.2.2 The response rate in the non-target lesions (if applicable) will be measured according to RECIST 1.1 (Section 7.1.3).
- 5.2.3 The duration of response at the target lesion will be defined as the duration from the time measurement criteria are met for CR or PR (whichever is first recorded) until the first date of recurrent or progressive disease as defined in Section 7.1.4.

Quad-Shot Radiotherapy in Combination with Immune Checkpoint Inhibition for  
Advanced/Recurrent Head and Neck Cancer  
Wake Forest Baptist Comprehensive Cancer Center  
WFBCCC60320

- 5.2.4 Progression-free survival (PFS) will be defined as in Section 7.1.5.
- 5.2.5 Overall survival (OS) will be defined as in Section 7.1.5.
- 5.2.6 Tolerability will be measured using the Patient-Reported Outcomes version of the Common Terminology Criteria for Adverse Events (PRO-CTCAE).

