### 2.1 Primary Objective(s)

2.1.1 Measure the overall response rate for immunotherapy given with quad-shot radiotherapy

### 2.2 Secondary Objective(s)

2.2.1 Measure the response rate at the target lesion.

Quad-Shot Radiotherapy in Combination with Immune Checkpoint Inhibition for  
Advanced/Recurrent Head and Neck Cancer  
Wake Forest Baptist Comprehensive Cancer Center  
WFBCCC60320

- 2.2.2 Measure the response rate at non-target sites *in patients with non-target sites.*
- 2.2.3 Evaluate the durability of response at the target lesion.
- 2.2.4 Evaluate progression-free survival.
- 2.2.5 Evaluate overall survival.
- 2.2.6 Assess the tolerability of the combination of quad-shot radiotherapy with immunotherapy in order to assess the feasibility of this treatment regimen.

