### 7.1.3 Response Criteria

- **Definition of complete response (CR)** for target and non-target lesions, as appropriate
  - Target Lesions:
    - Disappearance (or decrease to the point at which measurement is not possible) of all target lesions. **Any pathological lymph nodes (whether target or non-target) must have reduction in short axis to <10 mm** (the sum may not be “0” if there are target nodes)
  - Non-target lesions:
    - Disappearance (or decrease to the point at which measurement is not possible) of all non-target lesions. **All lymph nodes must be non-pathological in size (< 10 mm short axis)**
- **Definition of partial response (PR)** for target and non-target lesions, as appropriate
  - Target lesions:
    - At least a 30% decrease in the sum of diameters of target lesions, taking as reference the baseline sum of diameters
  - Non-target lesions
    - **Non-CR/Non-PD:** Persistence of 1 or more **non-target lesion(s)**.
- **Definition of progressive disease (PD)** for target and non-target lesions, as appropriate
  - Target Lesions:
    - > 20% increase in the sum of the longest diameters (SLD) taking as reference the smallest SLD recorded since the treatment started (nadir) **and minimum 5 mm increase over the nadir**
    - When sum becomes very small, increases within measurement error (2-3 mm) can lead to 20% increase
    - (Note: the appearance of one or more new lesions is also considered progressions)
  - Non-target lesions:
    - *Unequivocal progression* of existing non-target lesions. The appearance of one or more new lesions.
    - *Unequivocal progression* should not normally trump target lesion status. It must be representative of overall disease status change, not a single lesion increase
    - Although a clear progression of “non-target” lesions only is exceptional, the opinion of the treating physician should prevail in such circumstances, and the progression status should be confirmed at a later time by the review panel (or Principal Investigator).

- **Definition of stable disease (SD)** for target and non-target lesions, as appropriate
  - Target lesions:
    - Neither sufficient shrinkage to qualify for PR nor sufficient increase to qualify for PD, taking as reference the smallest sum diameters while on study
- **Definition and evaluation of best overall response**, if applicable  
The best overall response is the best response recorded from the start of the treatment across all time points.

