#### 7.1.4 Duration of Response

Duration of overall response: The duration of overall response is measured from the time measurement criteria are met for CR or PR (whichever is first recorded) until the first date that recurrent or progressive disease is objectively documented by clinical, radiographic, or pathologic findings (taking as reference for progressive disease the smallest measurements recorded since the treatment started).

The duration of overall CR is measured from the time measurement criteria are first met for CR until the first date that progressive disease is objectively documented.

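### Target-lesion duration of response (5.2.3) borrows its end event from the overall-response definition in 7.1.4, so the text does not settle whether new disease elsewhere ends it

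*Combined protocol and SAP*

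**What the plan says.** Objective 2.2.3 reads: "Evaluate the durability of response at the target lesion". Section 7.1.1 defines target lesions as the lesions, at most two, chosen for quad-shot radiotherapy; all others are non-target.

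Outcome 5.2.3 sets the start: "The duration of response at the target lesion will be defined as the duration from the time measurement criteria are met for CR or PR". The end is delegated; the duration runs "until the first date of recurrent or progressive disease as defined in Section 7.1.4".

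Section 7.1.4 has no target-lesion entry. It begins "Duration of overall response: The duration of overall response is measured from the time measurement criteria are met for CR or PR" and ends the duration when "recurrent or progressive disease is objectively documented by clinical, radiographic, or pathologic findings". Its second paragraph covers overall CR.

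Under the target-lesion entry for progressive disease, Section 7.1.3 adds that "the appearance of one or more new lesions is also considered progressions".

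Section 11.2 analyses duration among responders by a mean with a 95% confidence interval and a median with an interquartile range. It names Kaplan-Meier for PFS and OS only. For duration of response it gives no site-specific end event, no censoring rule and no rule for death.

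**The concern.** Objective 2.2.3 asks about the treated site. If a lung metastasis ends the duration while the irradiated lesion is still in response, the outcome measures freedom from progression anywhere after a target response. PFS already covers progression anywhere, so no time-to-event outcome would then isolate the irradiated lesion.

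The case is not remote. Metastatic disease is eligible (3.1.1.3). Section 6.4 stops treatment for progression only when local therapy cannot deal with it. A patient can therefore progress elsewhere and stay on scheduled scans with a controlled target, and the later target measurements would go unused.

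Poor durability at the treated site is also part of the rationale in Section 1.1, which reports median control in CR/PR patients of 5.7 months at the primary and 5.2 months at nodal sites after quad-shot radiotherapy. Two analysts following the present text could report different durations from the same data.

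**Working it through.** **Plan's own figure.** The plan states no estimate or precision for duration of response. Its only precision figure is the maximum 95% Clopper-Pearson width of 0.52 for a response rate with 15 patients (11.3). It reproduces: at 7/15 the limits are 0.213 and 0.734, a width of 0.52. This point does not touch it.

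**Which end event does the text give?**

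| Place | Bearing on the end event |
|---|---|
| 2.2.3, opening of 5.2.3 | Target lesion |
| End of 5.2.3 | Sent to 7.1.4 |
| 7.1.4 | Overall response and overall CR; no site named |
| 7.1.3, target-lesion PD entry | Growth of the target sum, plus a note that new lesions are progression |
| 7.1.3, best-overall-response table | Target status, non-target status and new lesions in separate columns; a new lesion gives overall PD whatever the target status |
| 11.2 | Silent |

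The first and fifth rows favour a target-only event. The third and fourth favour progression anywhere. Nothing says which prevails.

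**Direction.** Let T be a responder's time to target progression and E the time to progression elsewhere. The literal reading records min(T, E), which never exceeds T. It is strictly shorter whenever E comes first. No distributional assumption is needed.

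**Size, as illustration only.** Assume independent constant hazards λ_T (target) and λ_E (elsewhere), and let s = λ_E / (λ_T + λ_E).

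- Target-only median: ln 2 / λ_T.
- Median of min(T, E): ln 2 / (λ_T + λ_E) = (1 − s) × target-only median.

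The documents do not give s, so a range is assumed. The starting medians are the 5.7 and 5.2 months in Section 1.1.

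| Assumed s | From 5.7 months | From 5.2 months |
|---|---|---|
| 10% | 5.7 × 0.90 = 5.13 | 5.2 × 0.90 = 4.68 |
| 20% | 5.7 × 0.80 = 4.56 | 5.2 × 0.80 = 4.16 |
| 50% | 5.7 × 0.50 = 2.85 | 5.2 × 0.50 = 2.60 |

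The same model can start from an assumed median m to progression elsewhere, using 1 / (1/5.7 + 1/m). For m = 6, 12, 24 and 48 months the result is 2.92, 3.86, 4.61 and 5.09 months. The implied s is 48.7%, 32.2%, 19.2% and 10.6%, so the two routes cover nearly the same range.

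**The case against.** The strongest reply is that this is loose cross-referencing. Outcome 5.2.3 names the target lesion in its opening words. Section 7.1.4 takes the smallest recorded measurements as its reference for progression, and Section 7.1.1 does not require non-target lesions to be measured, so that wording suits target lesions. The table in 7.1.3 keeps target status apart from new lesions. This stands in part: a target-only reading is available. It does not remove the problem, because the section that 5.2.3 points to defines only overall response and the new-lesion note sits inside the target-lesion entry.

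A reader might go further and infer three things that the documents do not support.

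- *That target-lesion duration definitely ends at overall progression.* That is the literal reading, but not the only one.
- *That the median would be understated by a known amount, such as 5.7 read as 4.0 months.* This takes 30% of first progressions to be elsewhere, from 17.9 / (17.9 + 42.5) = 0.296 in Section 1.1. Those figures are causes of death in head and neck cancer, not sites of first progression in target-lesion responders, and locoregional is wider than the irradiated lesion. Nor can net bias against true local durability be sized: scans come about every 15 weeks (5 cycles of 3 weeks), which delays recorded progression, and 11.2 has no rule for responders who die or have not progressed.
- *That a corrected duration would be comparable with 5.7 months.* Section 1.1 does not give that figure's start point, end event or handling of distant failure.

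The consequence is also limited: this is one of six descriptive secondary outcomes in a pilot without hypothesis tests.

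**Conclusion.** The point holds as a conflict between the stated objective and the end event to which 5.2.3 refers. On the literal reading, duration can only be shortened relative to a target-only duration, and is shortened for every responder who progresses elsewhere first. On the target-only reading there is no shortening, but the text must then say so.

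The size is unknown. The illustrated range of about 5.1 to 2.9 months rests on a 5.7-month local median, constant independent hazards and an assumed 10% to 50% of the hazard lying elsewhere. It is not a forecast. The change should be made because the outcome otherwise may not answer objective 2.2.3. The primary overall response rate and its precision are unaffected.

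**What to change.** 1. In 5.2.3, end target-lesion duration at progression of the irradiated lesions only: the protocol's own threshold of more than 20% and at least 5 mm over nadir in the target sum, or recurrence there. State that the new-lesion note in 7.1.3 and non-target progression do not end it.
2. Censor at the last target-lesion assessment, and state how death without local progression is handled, for example as a competing event.
3. In 11.2, replace the raw mean and interquartile range for this outcome with a matching time-to-event estimator: Kaplan-Meier if death is censored, cumulative incidence if it competes.
4. Report overall duration of response under 7.1.4 as a separate result.

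The cost is mainly wording in 5.2.3, 7.1.3 and 11.2, with no change to sample size or scheduled on-treatment imaging. The downside is that imaging after study treatment is discretionary (6.5), so some patients will be censored locally after distant progression. Recording target-site status from later scans where they exist would limit this, at the price of some extra data collection. With at most 15 evaluable patients, and only the responders contributing, the estimate will be imprecise whichever estimator is used.

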Gamez et al.	14.8 Gy / 4	CR: 24% PR: 62%	Mucositis/xerostomia G2: 35%	1-3 cycles delivered with 3-4 weeks between cycles. Concurrent carboplatin or cetuximab administered 1 hour prior to the first fraction of each cycle.

However, the quad-shot regimen is not sufficient to provide a definitive dose for durable disease control. The equivalent dose in 2-Gy fractions (EQD2) (assuming  $\alpha/\beta=10$  [tumor]) for a single cycle is 16.9 Gy, 33.8 Gy for 2 cycles, and 50.7 Gy for 3 cycles. In prior studies, approximately

Quad-Shot Radiotherapy in Combination with Immune Checkpoint Inhibition for  
Advanced/Recurrent Head and Neck Cancer  
Wake Forest Baptist Comprehensive Cancer Center  
WFBCCC60320

64% of patients are eligible to receive more than one quad-shot cycle, and palliative response rates correlate with number of cycles delivered: 55% for 1 cycle, 44% for 2 cycles, 88% for 3 cycles (correlation coefficient 0.29, p=0.012) (18). Despite its fairly favorable rates of achieving palliation at the treated site, this palliative (rather than curative) regimen is insufficient for long-term disease control at the target site. Duration of control (DOC) has been reported in a phase II study also included in Table 2 (19). Median DOC was 5.7 months at the primary and 5.2 months at nodal sites for those with CR/PR and 1.8 months at the primary and 9.5 months at nodal sites for those with stable disease. Considering that advancements in systemic therapy using ICI have prolonged median survival for this patient cohort to 12 months or more, most patients will experience local and/or regional progression that may result in significant morbidity or even mortality. Therefore, there is strong rationale for combination therapy with PRT + immunotherapy for both patients with recurrent, advanced, incurable local disease or metastatic disease with an untreated primary.

Rationale for the Combination of Quad-Shot Radiotherapy and Immunotherapy

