#### 7.1.5 Survival Outcomes

Progression-Free Survival is defined as the duration of time from registration to the time of progression, death, or date of last contact; those lost to follow-up will be censored.

Overall Survival is defined as the duration of time from registration to date of death or date of last contact; those lost to follow-up will be censored.

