### 11.2 Analysis of Secondary Objective

There are 6 secondary outcomes of interest for this pilot study. These are 1) response rate for the target lesion; 2) response rate for non-target lesions 3) duration of response for the target lesion 4) progression free survival (PFS) 5) overall survival (OS) and tolerability assessed using PRO-CTCAE. We now describe our analytic approach for each measure.

For the response rate measures we will estimate the percent of responders (PR or CR) and the corresponding 95% Clopper Pearson exact confidence intervals. For the duration of response, among responders we will estimate both the mean and median duration and the corresponding 95% confidence intervals for the mean and inter-quartile range for the median. For time to event measures (PFS and OS) we will estimate Kaplan Meier survival curves and estimate the median time to event times as well as the percent PFS and OS at 6 months and 1 year post treatment. For tolerability, we will estimate the percent of patients with different AEs assessed using the PRO-CTCAE and corresponding 95% Clopper Pearson exact confidence intervals.

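### Duration of response at the target lesion has no rule for death or for a response still ongoing at last contact, so those responders have no value in the planned mean and median

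*Combined protocol and SAP*

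**What the plan says.** Section 5.2.3 starts duration of response at the target lesion when CR or PR is first recorded and runs it "until the first date of recurrent or progressive disease as defined in Section 7.1.4". Section 7.1.4 is written for the duration of overall response and runs it "until the first date that recurrent or progressive disease is objectively documented by clinical, radiographic, or pathologic findings". Neither section mentions death, last contact or censoring.

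Section 7.1.5 does deal with these for the survival outcomes. PFS is measured "from registration to the time of progression, death, or date of last contact", with patients lost to follow-up censored, and OS has a parallel rule. Nothing extends those rules to duration of response.

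Section 11.2 says that "among responders we will estimate both the mean and median duration", with a 95% confidence interval for the mean and an interquartile range for the median. Kaplan-Meier is assigned elsewhere: "For time to event measures (PFS and OS) we will estimate Kaplan Meier survival curves". Duration of response is not on that list.

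Under target-lesion progression, Section 7.1.3 adds that "the appearance of one or more new lesions is also considered progressions".

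**The concern.** A raw mean or median needs a completed duration for every responder. Two groups cannot supply one: responders who die with no documented progression, and responders who are alive and still in response when last seen. As written, the analysis either omits them or leaves the analyst to choose a rule after seeing the data.

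Changing the summary to Kaplan-Meier would not settle the matter alone. The definition must still say whether death is an event, a competing event or a censoring time. Sections 5.2.3 and 7.1.4 also leave open whether progression away from the irradiated lesion ends a response that is labelled as being at the target lesion.

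Durability at the target is a named objective (2.2.3). The Introduction gives poor long-term control at the treated site as a reason for the combination. With few responders, the handling of a few deaths can move the reported figure.

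**Working it through.** **Plan figures.** The documents give no share of responders expected to die without progression, so there is nothing to reproduce on this point. The only design figure, the maximum exact interval width of 0.52 in Section 11.3, does reproduce (7/15 gives 0.2127 to 0.7341, width 0.5215). It does not bear on duration.

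**Inputs from the documents**
- Median duration of control in CR/PR after quad-shot alone: "Median DOC was 5.7 months at the primary and 5.2 months at nodal sites for those with CR/PR" (Introduction). I use 5.7 months; 5.2 gives slightly lower shares.
- Median survival with checkpoint inhibition: 12 months or more (Introduction). I use 12.
- Causes of death: locoregional 42.5%, distant 17.9% (Section 1.1). So 57.5% are not locoregional, and 100 − 42.5 − 17.9 = 39.6% are neither.

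**Assumptions that are mine.** Times to target progression and to death are independent and exponential. A fraction *s* of the death hazard can act before target progression: *s* = 1 (all deaths), 0.575 (non-locoregional only) or 0.396 (neither cause).

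**Formulas.** Progression hazard λp = ln2/5.7 = 0.1216 per month. Death hazard λd = *s* × ln2/12 = *s* × 0.0578. Total Λ = λp + λd.
- Share dying first = λd/Λ
- Median with death as an event = ln2/Λ
- Mean with death as an event = 1/Λ
- 12-month target progression:
  - deaths dropped: 1 − exp(−12Λ)
  - 1 minus Kaplan-Meier, deaths censored: 1 − exp(−12λp)
  - cumulative incidence: (λp/Λ)(1 − exp(−12Λ))

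| | *s* = 1 | *s* = 0.575 | *s* = 0.396 |
|---|---|---|---|
| Λ per month | 0.1794 | 0.1548 | 0.1445 |
| Share dying first | 32% | 21% | 16% |
| Median, death an event (months) | 3.9 | 4.5 | 4.8 |
| Median, death censored (months) | 5.7 | 5.7 | 5.7 |
| Mean, death an event (months) | 5.6 | 6.5 | 6.9 |
| Mean, death censored, 1/λp (months) | 8.2 | 8.2 | 8.2 |
| 12-month progression, deaths dropped | 88% | 84% | 82% |
| 12-month progression, 1 − Kaplan-Meier | 77% | 77% | 77% |
| 12-month progression, cumulative incidence | 60% | 66% | 69% |

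In this model, time to progression among those who progress first is also exponential with rate Λ. Dropping deaths therefore gives the same median and mean as counting death as an event. The two part company on the proportion who progress, where dropping deaths overstates target progression by 28 points at *s* = 1 (88 − 60) and 13 points at *s* = 0.396 (82 − 69). Section 11.2 does not plan a 12-month figure for this endpoint; it is used here only to show the size of the effect.

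**Longer survival.** With an assumed 18-month median, which is not in the documents, the shares dying first fall to 24%, 15% and 11%.

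**Patients affected.** At the 13% to 36% overall response in Section 11.3, 15 patients give about 2 to 5 responders. With 16% to 32% dying first, that is roughly 0.3 to 1.7 patients. At the 53% and 77% CR plus PR reported for radiotherapy alone in Table 2 of the Introduction, there would be about 8 to 11 responders and roughly 1 to 3.5 affected.

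**Ongoing responders.** The share with neither progression nor death at time *t* after response is exp(−Λ*t*). At *s* = 1 this is 58% at 3 months and 34% at 6 months; the smaller values of *s* give more. Section 11.5 expects follow-up for response to finish about 3 months after accrual ends, so an analysis near that date could find many responses still open.

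**The case against.** The strongest objection concerns size. A reader might infer that a quarter to a third of responders lack a value on the plan's own figures. The documents do not support that. The plan states no such share, and any percentage needs a model. The quarter needs a median survival of about 15 to 18 months, which appears nowhere. Using the whole death hazard ignores that 42.5% of deaths are attributed to locoregional disease, which would often follow target progression. The 5.7 months comes from quad-shot without immunotherapy, with no account of how deaths were handled, and the 12 months describes the cohort, not responders. All of this stands, and it is why the range starts at 16%.

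A reader might also infer that every responder who dies with the target controlled has no value. If Section 7.1.4 and the new-lesion note in 7.1.3 govern, progression at another site supplies an end date, and only deaths with no documented progression anywhere lack one. That stands too. It shows a second ambiguity, but it gives no rule for death.

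Nor do the possible rules all pull apart: dropping deaths and counting them as events agree on the mean and median in this model. They still differ on the proportion progressing.

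Lastly, death as an event is a choice of estimand. PFS and OS already count it, and deaths from other causes blur a local measure. This is fair, and is the reason for reporting cumulative incidence beside the composite. The endpoint is also one of six secondary outcomes in a 15-patient pilot without hypothesis tests, which limits the consequence without removing the gap.

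**Conclusion.** The gap is in the text and does not depend on any model: death and ongoing response have no rule for this endpoint, while Section 11.2 prescribes summaries that need a value for every responder. Its size rests on independent exponential times, 5.7-month median control and 12-month median survival. On those assumptions about 16% to 32% of responders die before target progression, and fewer if survival is longer or if any progression ends the response. The choice of rule moves the median between 3.9–4.8 and 5.7 months, and 12-month target progression between 60–69% and 82–88%. The change should be made. It is a completion of the definition of a secondary endpoint and does not affect the primary analysis.

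**What to change.** In Sections 5.2.3 and 7.1.4:
- State whether target-lesion progression or progression at any site ends the response.
- Define duration of response as time from first CR or PR to that progression or death from any cause, whichever comes first.
- Censor responders still in response at their last adequate tumour assessment.

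In Section 11.2, replace the raw mean and interquartile range with a Kaplan-Meier estimate of the median. For pure local control, report the cumulative incidence of target-lesion progression with death as a competing event, not 1 minus Kaplan-Meier.

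The cost is a few clauses and two standard estimators. Section 6.5 already follows patients until death, so no new data are needed. The stated duration may come out shorter, and the composite mixes non-local deaths into a local measure; the cumulative incidence alongside it deals with the second point.
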